2.9 Pharmacokinetic endpoints

Pharmacokinetic (PK) analyses were performed at the time of primary analysis and no further data have been collected. The analysis of PK data will not be repeated at the final analysis.

2.10 Patient-reported outcomes

Not applicable.

3 Sample size calculation

The sample size calculation was based on the primary analysis and is not applicable for the final analysis.

4 Change to protocol specified analyses

No change from protocol specified analysis was made.

5 Appendix

5.1 Imputation rules

5.1.1 Study drug

The following rule should be used for the imputation of date of last administration for a given study treatment component:

Scenario 1: If the date of last administration is completely missing and there is no EoT eCRF page and no death date, the patient is considered as on-going:

The patient should be treated as on-going and the cut-off date should be used as the last dosing date.

Scenario 2: If the date of last administration is completely or partially missing and the EoT eCRF page is available (prior to any death date or withdrawal of consent date, if available):

Case 1: The date of last administration is completely missing, and the EoT visit date is complete, then this latter date should be used.

Novartis	Confidential	Page 45
SAP Final Analysis HGG		CDRB436G2201

Case 2: Only Year (yyyy) of the dose end date is available and yyyy < the year of EoT date:

Use Dec31yyyy

Case 3: Only Year(yyyy) of the dose end date is available and yyyy = the year of EoT date:

Use EoT date

Case 4: Both Year(yyyy) and Month (mm) are available for the date of last administration, and yyyy = the year of EoT date and mm < the month of EoT date:

Use last day of the Month (mm)

All other cases should be considered as a data issue and the statistician should contact the data manager of the study.

After imputation, compare the imputed date with start date of that specific record, if the imputed date is < start date of that record:

Use the start date of that record

Patients with missing start dates are to be considered missing for all study treatment component related calculations and no imputation will be made. If the date of first administration is missing, then the date of last administration should not be imputed.

5.1.2 AE, concomitant medications and safety assessment date imputation

 Table 5-1
 Imputation of start dates (AE, CM) and assessments (LB, EG, VS)

Missing Element	Rule
day, month, and year	• No imputation will be done for completely missing dates
day, month	 If available year = year of study treatment start date then If stop date contains a full date and stop date is earlier than study treatment start date then set start date = 01JanYYYY Else set start date = study treatment start date. If available year > year of study treatment start date then 01JanYYYY If available year < year of study treatment start date then 01JulYYYY

Missing Element	Rule
day	 If available month and year = month and year of study treatment start date then If stop date contains a full date and stop date is earlier than study treatment start date then set start date= 01MONYYYY. Else set start date = study treatment start date. If available month and year > month and year of study treatment start date then 01MONYYYY If available month and year < month year of study treatment start date then 15MONYYYY

Table 5-2	Imputation of end dates (AE, CM)
Missing	Rule
Element	(*=last treatment date plus 30 days not > (death date, cut-off date, withdrawal of consent date))
day, month, and year	• Completely missing end dates (incl. ongoing events) will be imputed by the end date of the on-treatment period*
day, month	• If partial end date contains year only, set end date = earliest of 31DecYYYY or end date of the on-treatment period *
day	• If partial end date contains month and year, set end date = earliest of last day of the month or end date of the on-treatment period*

Any AEs and concomitant medications with partial/missing dates will be displayed as such in the data listings.

Any AEs and concomitant medications which are continuing as per data cut-off will be shown as 'ongoing' rather than the end date provided.

The above imputations are only used for analyses of time to and duration of AEs and concomitant medications, and for assigning pre/on/post treatment periods.

5.1.2.1 Other imputations

Incomplete date of initial diagnosis of cancer and date of most recent recurrence

Missing day is defaulted to the 15th of the month and missing month and day is defaulted to 01-Jan.

Incomplete assessment dates for tumor assessment

All investigation dates (e.g. MRI scan, CT scan) must be completed with day, month and year. If one or more assessment dates are incomplete but other investigation dates are available, this/these incomplete date(s) are not considered for calculation of the assessment date and assessment date is calculated as the latest of all investigation dates (e.g. MRI scan, CT scan) if the overall response at that assessment is CR/PR/SD/UNK. Otherwise – if overall response is

progression – the assessment date is calculated as the earliest date of all investigation dates at that evaluation number. If all measurement dates have no day recorded, the 1st of the month is used. If the month is not completed, for any of the investigations, the respective assessment will be considered to be at the date which is exactly between previous and following assessment. If a previous and following assessment is not available, this assessment will not be used for any calculation.

Applying the cut-off to tumor assessment

For tumor related assessments, if an evaluation has some assessments done prior to cut-off date and others after the cut-off date, then the evaluation is considered post-cut-off date and will be excluded from analysis.

5.2 AEs coding/grading

AEs are coded using the Medical dictionary for regulatory activities (MedDRA) terminology.

AEs will be assessed according to the CTCAE version 4.03.

The CTCAE represents a comprehensive grading system for reporting the acute and late effects of cancer treatments. CTCAE grading is by definition a 5-point scale generally corresponding to mild, moderate, severe, life threatening, and death. This grading system inherently places a value on the importance of an event, although there is not necessarily proportionality among grades (a grade 2 is not necessarily twice as bad as a grade 1).

5.3 Systemic corticosteroids

Systemic corticosteroids should be flagged based on a list provided by the clinical team. Further details will be provided in the programming datasets specifications (PDS).

The total daily dose can be calculated by multiplying the dose per administration by the factor specified in Table 5-3 according to the specified dosing frequency.

Meaning	Multiply dose per administration
Twice per day	2
Twice per week	0.2857
-	Set to missing
Once per day	1
-	1
-	Set to missing
As required	Set to missing
Once per day	1
Once per hour	24
Once every 2 hours	12
Once every 3 hours	8
Once every 4 hours	6
Once every 5 hours	4.8
Once every 6 hours	4
	Meaning Twice per day Twice per week - Once per day - - As required Once per day Once per day Once per hour Once every 2 hours Once every 3 hours Once every 4 hours Once every 5 hours

 Table 5-3
 Multiplicative factors to calculate total daily dose

Frequency	Meaning	Multiply dose per administration
Q8H	Once every 8 hours	3
Q12H	Once every 12 hours	2
Q14H	Once every 14 hours	1.7143
Q18H	Once every 18 hours	1.3333
Q24H	Once every 24 hours	1
QID	Four times per day	4
QM	Once per month	0.0328
Q2M	Once every 2 months	0.0164
Q3M	Once every 3 months	0.0110
QOD	Once every other day	0.5
QW	Once per week	0.1429
Q2W	Once every 2 weeks	0.0714
Q3W	Once every 3 weeks	0.0476
Q4W	Once every 4 weeks	0.0357
TID	Three times per day	3
TIW	Three times per week	0.4286
Unknown	-	Set to missing
Weekly	Once per week	0.1429
5x per day	Five times per day	5
6x per day	Six times per day	6
7x per day	Seven times per day	7
8x per day	Eight times per day	8

5.4 Laboratory parameters derivations

Grade categorization of lab values will be assigned programmatically as per NCI CTCAE version 4.03. The calculation of CTCAE grades will be based on the observed laboratory values only, clinical assessments will not be taken into account. The criteria to assign CTCAE grades are given in Novartis internal criteria for CTCAE grading of laboratory parameters. The latest available version of the document based on the underlying CTCAE version 4.03 at the time of analysis will be used.

For laboratory tests where grades are not defined by CTCAE v4.03, results will be graded by the low/normal/high (or other project-specific ranges, if more suitable) classifications based on laboratory normal ranges.

A severity grade of 0 will be assigned for all non-missing lab values not graded as 1 or higher. Grade 5 will not be used. For laboratory tests that are graded for both low and high values, summaries will be done separately and labelled by direction, e.g., sodium will be summarized as hyponatremia and hypernatremia.

Imputation Rules

CTC grading for blood differentials is based on absolute values. However, this data may not be reported as absolute counts but rather as percentage of white blood cells (WBC).

If laboratory values are provided as '<X' (i.e. below limit of detection) or '>X', prior to conversion of laboratory values to SI unit, these numeric values are set to X.

Novartis	Confidential	Page 49
SAP Final Analysis HGG		CDRB436G2201

The following rules will be applied to derive the WBC differential counts when only percentages are available for a xxx differential

xxx count = (WBC count) * (xxx %value / 100)

Further derivation of laboratory parameters might be required for CTCAE grading. For instance, corrected calcium can be derived using the reported total calcium value and albumin at the same assessment using the following formula:

Corrected Calcium (mg/dL) = Calcium (mg/dL) - 0.8 [Albumin (g/dL)-4]

In order to apply the above formula, albumin values in g/L will be converted to g/dL by multiplying by 0.1), calcium values in mmol/L will be converted to mg/dL by dividing by 0.2495. For calculation of laboratory CTC grades 0 and 1, the normal range for derived corrected calcium is set to the same limits (in mg/dL) as for calcium.

CTC grades for the derived absolute WBC differential counts (neutrophils, lymphocytes) and corrected calcium will be assigned as described above for grading

5.4.1 Growth data

SDS will be calculated using the current formulae provided by the WHO as follows:

- $\frac{\left(\frac{X}{M}\right)^{L}-1}{2}$
- 1. Calculate $z_{ind} = LS$
- $\begin{array}{ll} \text{2.} & \text{If} \mid z_{\text{ind}} \mid \leq 3, & \text{SDS} = z_{\text{ind}} \\ & \text{If} \; z_{\text{ind}} > 3, & \text{SDS} = 3 + (X \text{SD3}pos) \ / \ \text{SD23}pos \\ & \text{If} \; z_{\text{ind}} < -3, & \text{SDS} = -3 + (X \text{SD3}neg) \ / \ \text{SD23}neg \\ \end{array}$

where:

- X is height in centimeters or BMI in kilograms/ m^2 ,
- *L*, *M* and *S* are height or BMI-, sex- and age-specific reference values from the WHO Growth Charts.
- SD3*pos* is the cutoff 3SD calculated by the LMS method: SD3*pos* = M * $(1 + LS*3)^{1/L}$
- SD3*neg* is the cutoff -3SD calculated by the LMS method: SD3*neg* = M * $(1 + LS^*(-3))^{1/L}$
- SD23*pos* is the difference between the cutoffs 3SD and 2SD: SD23*pos* = M * $(1 + LS*3)^{1/L}$ - M * $(1 + LS*2)^{1/L}$
- SD23*neg* is the difference between the cutoffs -2SD and -3SD: SD23*neg* = M * $(1 + LS^*(-2))^{1/L}$ - M * $(1 + LS^*(-3))^{1/L}$

Height-for-age and BMI-for-age L, M and S reference values for males and females are available under [http://www.who.int/childgrowth/standards/en/] (for patients aged between 0 to 5 years old) and [http://www.who.int/growthref/en/] (for patients aged between 5 to 19 years old). Note: use age in months at time of assessment "(visit date – date of birth) / 30.4375" rounded to the nearest whole month for corresponding values of L, M and S. These correspond to the latest available international references available at this time and described in the 2007 Bulletin of the WHO [Mercedes de Onis et al 2007]. SDS is actually a Z score that measures the distance from the population mean in units of standard deviations. That is, SDS < 0 refers

Novartis	Confidential	Page 50
SAP Final Analysis HGG		CDRB436G2201

to values lower than the population mean, and for example SDS \leq -1.645 refers to values in the lowest 5%.

The SDS score can be converted to a percentile assuming a standard normal distribution [mean=0, standard deviation =1]. Note that BMI is reported instead of weight as no reference data are provided by the WHO for age beyond 10.

Height velocity is defined as follows:

Height velocity (cm/6-months) = (height in time window k – height in time window k-1) ÷ ([assessment date in time window k – assessment date in time window k-1] ÷ [365.25/2]), and similarly for weight velocity.

Velocity SDS is calculated as (velocity – mean) / standard deviation, where mean and standard deviation are obtained as the height-, weight-, sex- and age-specific values [Baumgartner et al 1986], where the age category immediately above the patient's exact age (at the assessment date in time window k) should be used. Velocity SDS will only be calculated for time window k if data also exists for time window k-1, since calculating across multiple units of 6 months requires more than one reference value to be taken into account.

Table 5-4 summarizes the time windows for growth data, where windows are centered at every 6 months after start of study treatment. Although height and weight are collected more frequently than every 6 months (post-enrollment), this choice of time window length was made to reflect the degree of accuracy in the reference values (every 6 months) that will be used in the calculation of summary variables of growth.

In case of multiple assessments falling into the time window interval, the closest to the target date will be considered. For example, If there are three assessments falling under the time window of Day 85 to 252, then the closest one to target day of 168 will be considered. If two assessments are equidistant from target date, the average will be considered of those respective assessments.

Planned assessment	Time window
Baseline	Days ≤1
Month 6 (Day 168)	Days 85 – 252
Month 12 (Day 336)	Days 253 – 420
Month 18 (Day 504)	Days 421 – 588
Month xx (Day xx * 28)	Days ((xx – 3) * 28 + 1) – Day ((xx + 3) * 28)
End of treatment (EoT)	Earliest data available on or after EoT date up to and including 30 days after EoT
Day 1 = date of first intake of study drug	
xx = Every 6 months	

Table 5-4Time windows for growth data (height SDS, height velocity, weight velocity, BMI SDS)

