2.8.4.7 Growth and development (Height and Weight)

Growth data consist of height, BMI, height SDS, BMI SDS, height velocity SDS, weight velocity SDS, height velocity and weight velocity.

Height and weight will be summarized at 6-month intervals during the on-treatment period, using the standard deviation scores (SDS, also called Z-score), velocity and velocity SDS. The relevant height and weight values for each 6-month period are defined using time windows, as defined in Table 5-4. The Z-scores will allow identification of potential outliers.

The formula used to calculate the SDS and height and weight velocities are provided in the Appendix 5.4.2.

Novartis	Confidential	Page 42
SAP Final Analysis HGG		CDRB436G2201

Note that BMI SDS are reported instead of weight SDS as no reference data for weight are provided by the WHO for age beyond 10.

Height and BMI SDS and height and weight velocity SDS will be summarized using descriptive statistics (mean, standard deviation, median, Q1, Q3, minimum, maximum) for each time window (at baseline and thereafter allowing informal comparison of growth data), as well as by presenting number of patients with SDS values lower/higher than 5th/95th percentiles respectively.

Box plots will be plotted for each time window. A shift table to compare baseline SDS to the worst on-treatment SDS categorized as Low (SDS < -1.645), High (SDS > 1.645) or Normal (-1.645 \leq SDS \leq 1.645) will be produced for height and BMI SDS. Another shift table to compare the baseline height SDS to the last available on-treatment height SDS categorized according to the main percentile lines (>95th, 95th to 90th, 90th to 75th, 75th to 50th, 50th to 25th, 25th to 10th, 10th to 5th and \leq 5th percentile) will be produced.

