Height velocity (cm/6-months) = (height in time window k – height in time window k-1) ÷ ([assessment date in time window k – assessment date in time window k-1] ÷ [365.25/2]), and similarly for weight velocity.

Velocity SDS is calculated as (velocity – mean) / standard deviation, where mean and standard deviation are obtained as the height-, weight-, sex- and age-specific values [Baumgartner et al 1986], where the age category immediately above the patient's exact age (at the assessment date in time window k) should be used. Velocity SDS will only be calculated for time window k if data also exists for time window k-1, since calculating across multiple units of 6 months requires more than one reference value to be taken into account.

Table 5-3 summarizes the time windows for growth data, where windows are centered at every 6 months after start of study treatment. Although height and weight are collected more frequently than every 6 months (post-enrollment), this choice of time window length was made to reflect the degree of accuracy in the reference values (every 6 months) that will be used in the calculation of summary variables of growth.

In case of multiple assessments falling into the time window interval, the closest to the target date will be considered. For example, if there are three assessments falling under the time window of Day 85 to 252, then the closest one to target day of 168 will be considered. If two assessments are equidistant from target date, the average will be considered of those respective assessments.

Table 5-4	Time windows for growth data (height SDS, height velocity, weight
	velocity, BMI SDS)

Planned assessment	Time window	
Baseline	Days ≤1	
Month 6 (Day 168)	Days 85 – 252	
Month 12 (Day 336)	Days 253 – 420	
Month 18 (Day 504)	Days 421 – 588	
Month xx (Day xx * 28)	Days ((xx – 3) * 28 + 1) – Day ((xx + 3) * 28)	
End of Treatment (EoT)	Earliest data available on or after EoT date up to and including 30 days after EoT	
Day 1 = date of first intake of study drug		
xx = Every 6 months		

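### Table 5-4 of both final SAPs applies an end-of-treatment row to height and weight velocity with no minimum interval, so EoT velocity is scaled to 6 months from gaps that are usually much shorter

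*SAP*

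**What the plan says.** The wording below is from the HGG final SAP; the LGG final SAP has the same formula, table title and EoT row in its Section 5.4.1.

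- The title of Table 5-4 names the variables it governs: "Time windows for growth data (height SDS, height velocity, weight velocity, BMI SDS". Velocity is listed with the two SDS measures.
- The rows are baseline, Month 6, 12, 18 and so on in 6-month steps, and EoT, defined as "Earliest data available on or after EoT date up to and including 30 days after EoT". Table 5-3 of the 2021 SAPs (HGG Amendment 2, LGG Amendment 1) had no EoT row.
- The denominator of velocity is the elapsed time expressed in half-years: "assessment date in time window k – assessment date in time window k-1] ÷ [365.25/2".
- The one condition on velocity SDS is: "Velocity SDS will only be calculated for time window k if data also exists for time window k-1". The reason given concerns gaps spanning several 6-month units, that is, gaps that are too long.
- Within a month window the choice of record is: "In case of multiple assessments falling into the time window interval, the closest to the target date will be considered". The EoT record is not excluded.
- On window length, Section 5.4.1 says that "this choice of time window length was made to reflect the degree of accuracy in the reference values (every 6 months").

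Section 2.8.4.7 then reports velocity by window: "Height and BMI SDS and height and weight velocity SDS will be summarized using descriptive statistics", as well as "presenting number of patients with SDS values lower/higher than 5th/95th percentiles respectively".

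**The concern.** The regular windows are spaced so that an observed velocity can be compared with a 6-monthly reference mean and SD. The EoT row is tied to the day treatment stops, not to a 6-month target. If the table is programmed as titled, EoT velocity is the change since the preceding window, however recent, stretched to 6 months and divided by a 6-monthly reference SD. Ordinary measurement error in height or weight is stretched by the same factor. The EoT column would then show more very low and very high velocity SDS values than growth itself produces, in the safety report of a paediatric trial.

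If the EoT record is also the one closest to the target of its month window, the two dates coincide and velocity cannot be computed. The SAP does not say which treatment of the record applies.

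**Working it through.** **1. The plan's windows reproduce.** Days (xx−3)×28+1 to (xx+3)×28 give 85–252, 253–420 and 421–588 for xx = 6, 12, 18, as printed.

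**2. Planned measurement days.** Height and weight are vital signs, so Table 2-2 applies: days 1, 8, 15, 22, 29, 50, then 106, 162, 218, 274, 330, 386, then 498, 610 and every 112 days. The closest-to-target rule selects days 1, 162, 330 and 498 for baseline and Months 6, 12 and 18. Regular gaps are therefore 161, 168 and 168 days, and the scaling factor 182.625/gap is 1.13, 1.09 and 1.09.

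**3. Gap at EoT.** I placed the EoT record on each of the 504 days from 85 to 588, kept the planned visits before it, and took the gap to the latest filled window.

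| | EoT record kept out of month windows | EoT record may fill its month window |
|---|---|---|
| Range of gap | 1–168 days | 0–90 days |
| Exactly zero | 0 | 267/504 = 53% |
| 28 days or less | 140/504 = 28% | 318/504 = 63% (including zeros) |
| 90 days or less | 389/504 = 77% | 504/504 = 100% |
| 150 days or more | 19/504 = 4% | 0 |

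These are shares of possible EoT days, not forecasts of patients; the documents give no distribution of EoT.

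The preceding window does not always hold the last visit. For EoT on day 400 the last visit is day 386, but the Month 12 record is day 330, so the gap is 70 days, not 14.

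**4. Amplification of error (arithmetic only).** Factor = 182.625/gap: 13.0 at 14 days, 6.5 at 28, 3.3 at 56, 2.0 at 90, 1.09 at 168. For example, an error of 0.5 cm in a height difference becomes 0.5 × 6.52 = 3.3 cm per 6 months at 28 days and 0.5 × 1.087 = 0.54 at 168 days.

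**5. Illustration of the effect on the percentile counts.** The documents give neither the measurement error s per reading nor the reference SD r. I assumed s = 0.2–0.5 cm and r = 0.75–1.5 cm per 6 months. The error SD of velocity is e = √2 × s × 182.625/gap. A normally growing child falls outside the 5th to 95th percentiles with probability 2 × [1 − Φ(1.645 × r/√(r² + e²))].

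With s = 0.3 and r = 1.0:

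- Gap 28 days: e = 1.414 × 0.3 × 6.52 = 2.77, and the probability is 58%.
- Gap 168 days: e = 0.46, and the probability is 13.5%.

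Over the whole assumed range it is 30–79% at 28 days, 12–45% at 90 days and 11–25% at 168 days, against 10% with no error.

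**The case against.** The best defence is that EoT velocity was never intended. Section 2.8.4.7 speaks of summaries at 6-month intervals, Section 5.4.1 describes windows centred every 6 months, and the condition on the preceding window is justified in 6-month units. On that reading k and k−1 are successive month windows and EoT has no place in the sequence. Nearly the same EoT row stands in Tables 2-1, 2-2, 2-3 and 5-6, so it may be a standard row carried into a table whose title covers four variables jointly.

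This stands as an account of likely intent. It does not settle the rule: the title names velocity, no sentence removes it from the EoT row, and a programmer following the table would produce it. If the defence is right, the footnote merely records the intent.

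It is also fair that the regular windows are not exactly 6 months apart. After Month 18, with 16-weekly visits, the selected days are 722, 834 and 1058, so gaps run from 112 to 224 days. None of these approaches the gaps at EoT.

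A reader might infer that zero gaps create false growth abnormalities. They do not: a zero gap leaves velocity undefined, hence missing. Zero gaps arise only if the EoT record may fill its month window, whereas most gaps of a few days arise only if it may not. The two should not be added together.

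**Conclusion.** The point holds as a defect in a stated rule. Under either treatment of the EoT record, the gap behind EoT velocity is usually far below the 6 months for which the reference values are meant: 90 days or less on 77% of EoT days, or 0 to 90 days with about 53% undefined. These figures rest only on the SAP's windows, formula and planned visits, with EoT on days 85 to 588. That short gaps inflate the EoT counts beyond the 5th and 95th percentiles follows from the formula. By how much does not: the percentages in step 5 of the working rest on assumed measurement error and reference SD, and the ranges at 90 and 168 days overlap.

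The reach is limited to descriptive velocity and velocity SDS output at EoT. Height SDS and BMI SDS are not affected, nor are the growth shift tables, which use those two measures. Because LGG chemotherapy is a fixed course and dabrafenib plus trametinib is open-ended, a reader might infer a biased comparison of growth between arms. The documents do not support that for the specified model, which uses height SDS (LGG final SAP, Section 5.5.5). No efficacy result or hypothesis test is involved.

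**What to change.** In Table 5-4 of both final SAPs, add a footnote stating that the EoT row applies to height SDS and BMI SDS only, and that height velocity, weight velocity and their SDS are calculated only between successive 6-month windows. This also removes the need to settle, for EoT velocity, whether the EoT record may fill a month window.

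The cost is one footnote in each SAP and one program condition; no collected data and no SDS result are lost. The downside is that no EoT velocity is reported.
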